## **1.0 Background**

Infantile hypertrophic pyloric stenosis is a condition caused by marked hypertrophy and hyperplasia of the muscular layers of the pylorus. Pyloric stenosis occurs in approximately 1 out of every 300 live births in the United States. The highest incidence is in first born male children, specifically those who had an affected parent. The age of presentation ranges from 3 to 12 weeks, with 95% presenting at 8 weeks. Infants exhibit symptoms of non-bilious, projectile vomiting shortly after feeding. Pyloric stenosis can mimic failure to thrive and results in a hypochloremic, hyponatremic, metabolic alkalosis, and in severe cases of dehydration, metabolic acidosis. Treatment requires surgical pyloromyotomy.

During induction of anesthesia for the surgical pyloromyotomy, direct laryngoscopy is the primary method for securing an airway in the operating room. Any infant with the diagnosis of pyloric stenosis is considered to be at risk for aspiration of gastric contents, and therefore, requires a rapid sequence intubation for securing the airway. Rapid sequence intubation is challenging in infants and leads to frequent oxygen desaturation, perhaps even more frequent at a teaching institution, where resident anesthesiologists are securing the airway. With the introduction of the video laryngoscope, the staff anesthesiologist is able to have direct vision as the resident anesthesiologist secures the airway. This allows for early advice and intervention by the staff anesthesiologist. We hypothesize that the video laryngoscope will have a decreased incidence of oxygen desaturation when compared to conventional laryngoscopy in this patient population.

## **2.0 Rationale and Specific Aims**

Specific Aims of this study include determining if there is a difference in the desaturation rates of the two different intubation techniques. Also, is there is a difference in intubation success between the two techniques, does intubation success vary with different training levels, and does desaturation rate differ amongst training levels.

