#### **4.0 Study Procedures**

1. **Study design:** The study will be randomized, controlled, and prospective in design.
2. **Comparison groups** The two comparison groups will be:
  - a. **Conventional Laryngoscopy (DL), N = 35**  
Endotracheal intubation will be performed by conventional direct laryngoscopy.
  - b. **Video Laryngoscopy (CMAC), N = 37**  
Endotracheal intubation will be performed by video laryngoscopy with the C-MAC.
3. **Study and timeline of interventions**
  - a. **Preoperative:** All patients enrolled in this study will receive an intravenous catheter preoperatively.
  - b. **Intraoperative:** Subjects will all undergo induction of anesthesia by rapid sequence intubation. Upon arrival to the operating room, a new pulse oximeter probe will be placed on the patient's big toe. Orogastic suctioning with a 10 French Salem sump will be done with the patient supine, right and left lateral positions. Preoxygenation with 100% oxygen will be undertaken for approximately one minute. After pre-oxygenation, a rapid sequence induction will occur with Propofol 2.5mg/kg and Succinylcholine 2.5mg/kg IV. The resident will two-hand mask the patient and the staff anesthesiologist will manually ventilate the patient maintaining airway pressures less than 15mmHG. Approximately twenty seconds after administration of succinylcholine, direct laryngoscopy with a Miller 1 blade or a CMAC 0 blade will be undertaken. The patient will be intubated with a 3.0 cuffed endotracheal tube that has been loaded with a stylet. If the resident is having difficulty securing the airway, the staff may intervene at any point. The airway will be deemed secure when end tidal CO2 x 3 is seen, chest rise is adequate, and bilateral and equal breath sounds are heard. Anesthesia will be maintained with sevoflurane. The patient will be extubated at the conclusion of the case when he/she meets extubation criteria.
  - c. **Postoperative:** All patients will receive routine PACU care. Pain and anxiety scores will be recorded according to routine PACU practice. Medication for pain, nausea, and anxiety will be given according to the judgment of the anesthesiologist.
  - d. **Measured end-points:**
    - i. Level of resident training
    - ii. Desaturation below 80% during induction

- iii. Staff intervention needed for intubation
- iv. Number of intubation attempts

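### Does leaving intubation success undefined let this secondary aim be answered in opposite ways?

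*Combined protocol and SAP*

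**What the plan says.** Section 2.0 (Rationale and Specific Aims) puts desaturation first and then adds questions on intubation success: "is there is a difference in intubation success between the two techniques" and "does intubation success vary with different training levels". It does not say what success means.

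Section 4.0 (Study Procedures) supplies three related pieces:

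- A completion criterion, beginning "The airway will be deemed secure when end tidal" and going on to chest rise and breath sounds. It does not depend on who placed the tube or after how many tries.
- A permission for takeover, the same in both arms: "If the resident is having difficulty securing the airway, the staff may intervene at any point".
- Two listed end-points: "Staff intervention needed for intubation" and "Number of intubation attempts".

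Section 7.0 (Statistical Considerations) says these items are recorded. Its only test and only power statement concern desaturation below 80%.

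Section 1.0 (Background) explains why the arms might differ. With video, "the staff anesthesiologist is able to have direct vision as the resident anesthesiologist secures the airway", and "This allows for early advice and intervention by the staff anesthesiologist".

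**The concern.** An aim without a defined outcome invites a choice after the data are seen. Here there are two obvious stand-ins, and the trial's own rationale suggests that they may diverge. If the shared view leads staff to help sooner, the video arm may show fewer attempts and more interventions. One analyst could then report that video is better (attempts), another that conventional laryngoscopy is better (unaided success), and a third that there is no difference (both combined).

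The attempts item has an ambiguity of its own: the document does not say whether a takeover during the first attempt starts a second one.

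At stake are the direction of the answer to a secondary aim and, if a reading were picked by its result, its false-positive rate.

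**Working it through.** **The plan's own figure.** Section 7.0 gives 36 per group for 30% against 5%, two-sided 0.05, 80% power. With pooled variance and no continuity correction:

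n = [1.96·√(2·0.175·0.825) + 0.8416·√(0.30·0.70 + 0.05·0.95)]² / 0.25² = (1.053 + 0.427)² / 0.0625 ≈ 35.1, rounded up to 36.

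Power at 36 is 81.1%. The odds ratio is (0.05/0.95)/(0.30/0.70) = 0.123, as stated. The figure reproduces and does not involve intubation success, for which the plan makes no power claim.

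**How the readings can move.** Classify each infant as:

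- a: one attempt, no intervention
- b: one attempt, with intervention
- c: two or more attempts, no intervention
- d: two or more attempts, with intervention

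Let a share s of the video arm move from one cell to another. The document gives no such shares, so s is assumed.

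| Assumed move with video | One attempt (a+b) | No intervention (a+c) | Combined (a) |
|---|---|---|---|
| c to b: early takeover, counted as the same attempt | +s | −s | 0 |
| c to d: early takeover, counted as a new attempt | 0 | −s | 0 |
| c to a: advice alone rescues the first attempt | +s | 0 | +s |
| d to b: staff already involved, fewer tries | +s | 0 | 0 |
| a to b: staff step in where the resident would have succeeded | 0 | −s | −s |

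Only the first row, taken alone, gives opposite signs. Mixtures can too, for example some infants moving c to a and others c to d.

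**Size.** For 2 to 4 infants of 36, s = 2/36 to 4/36 = 5.6 to 11.1 points, so under c to b the two items end up 2s = 11.1 to 22.2 points apart.

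The 95% half-width for an arm difference is 1.96·√(2p(1−p)/36): 23.1 points at p = 0.5 and 13.9 at p = 0.9. Section 4.0 lists 35 and 37 instead of 36 and 36. Since 1/35 + 1/37 = 0.0556 = 2/36 to that precision, the half-widths do not change.

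**Simulation under assumed cell shares** (36 per arm, uncorrected chi-square at 0.05):

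- c to b: one attempt is significant for video in 6.4% to 20.1% of trials, and no intervention is significant for conventional in 7.6% to 25.0%. Both occur in the same trial in at most 2.3%.
- c to d, same settings: one attempt is significant for video in 2.2% to 2.7%, which is chance level for one direction. Both occur in at most 0.05%.
- Identical arms: one fixed reading gives 3.8% to 5.9% false positives. Choosing afterwards between the two recorded items gives 8.2% to 10.9%, and among all three readings 9.1% to 12.5%.

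**A second model.** Suppose the resident succeeds with probability 0.60 per attempt and staff with 0.95, staff take over after two failed attempts with conventional and after one with video, and each staff try is a new attempt (all assumed).

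- Intervention: 0.4² = 16% against 40%.
- Mean attempts: 1 + 0.4 + 0.16/0.95 = 1.57 against 1 + 0.4/0.95 = 1.42.
- One-attempt rate: 60% in both arms.

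The conflict now appears in mean attempts and not at all in the one-attempt rate. Its presence and size depend on the model and on the summary chosen.

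**The case for a change.** The strongest case for a change is that two of the questions in section 2.0 rest on an undefined term, that the secure-airway criteria cannot separate resident from staff success, and that earlier staff involvement with video is the stated rationale and not a far-fetched scenario. Picking a reading by its result would roughly double the false-positive rate. One paragraph using items already collected would close the gap.

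Much of this stands. The definitions are absent, the attempts item is ambiguous, and opposite directions are possible.

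Three things weaken the step from there to a change:

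- The false-positive figures presuppose significance tests that section 7.0 does not plan for these items, and selective reporting of end-points that section 4.0 lists side by side.
- Fewer attempts with more staff help would not be a contradiction. It would be what the Background anticipates, and two separate estimates would show it.
- The natural single definition, first-attempt success with no staff intervention, is not clearly better. It stays fixed under c to b, but rises under c to a and falls under a to b. It also counts as failure the staff help that section 1.0 offers as a reason for video. Resident success and team success are both defensible targets.

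Nor is it right to say that takeover is unregulated. Section 4.0 permits it at staff discretion. Only its counting is unstated.

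**Conclusion.** The gap is real but minor, and no change to the plan follows. Section 2.0 names intubation success without defining it. Section 4.0 nevertheless commits the trial to recording both staff intervention and number of attempts, and a competent analyst would report each by randomised arm with its interval and state the counting convention used. Nothing written in the plan would produce a wrong result.

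Training level is not randomised and no power is claimed for it, so those comparisons would be read as descriptive in any case.

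The feared reversal of 11.1 to 22.2 points between the two items rests on an assumed shift of 2 to 4 infants per arm and on counting a first-attempt takeover as one attempt. With a takeover counted as a new attempt, or with advice alone doing the work, the reversal disappears. Even under the least favourable pattern, significant results in both directions occur in at most 2.3% of simulated trials. The primary comparison of desaturation below 80%, and its 36 per group, do not depend on any of this.

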## **3.0 Inclusion/Exclusion Criteria**

Inclusion Criteria:

- Need general anesthesia for pyloromyotomy procedure
- Have been informed of the nature of the study and informed consent has been obtained from the legally responsible guardian

Exclusion Criteria:

- Abnormal/difficult airway
- Allergy to succinylcholine and/or propofol

## **5.0 Enrollment/Randomization**

Patients will be enrolled in the study on the day of surgery, in a private setting- including but not limited to: pre-operative waiting area, pre-operative holding, or patient's hospital

room. The study will be explained by a member of the research team with extensive knowledge of the protocol. Randomization will occur for each patient using a computer randomized list to one of two groups. One group will be conventional laryngoscopy and the other will be video laryngoscopy. The study seeks to enroll 36 subjects to each group.

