## **7.0 Statistical Considerations**

The primary outcome of the study will be desaturation below 80%. Resident training level, staff intervention required, number of intubation attempts and any adverse events will also be recorded. Our hypothesis is a significantly smaller percentage of patients in the CMAC group will desaturate below 80% compared to the DL group. A two group chi-square test with a 0.05 two-sided significance level will have 80% power to detect the difference between 30% vs. 5% proportion of O2sat dropping below 80% (odds ratio of 0.123) when the sample size in each group is 36.

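### The intubating resident is not fixed before the arm is revealed, so the operator could be chosen knowing the device, and the planned analysis takes no account of training level

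*Combined protocol and SAP*

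**What the plan says.** Section numbers here are those printed on the body headings, which differ from the table of contents.

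- **Allocation.** Section 5.0 enrols infants on the day of surgery and states: "Randomization will occur for each patient using a computer randomized list to one of two groups". It does not say who holds the list, when the arm is revealed, or whether the operator has been named by then.
- **Operator.** Section 4.0 speaks only of the resident. It has no rule on who that is, at what level, or when chosen. The staff anesthesiologist is present and free to take over.
- **Why the operator matters.** Section 1.0 suggests that desaturation may be more common where residents secure the airway. Of the video device, which gives staff a view of the airway, it says: "This allows for early advice and intervention by the staff anesthesiologist". Two of the four aims in section 2.0 ask "does intubation success vary with different training levels, and does desaturation rate differ amongst training levels".
- **Use of training level.** "Level of resident training" is listed among the measured end-points in section 4.0, and section 7.0 says that it will be recorded. It is neither a stratification factor nor a covariate, and no analysis is given for the training-level aims.
- **Analysis.** Section 7.0 gives one test: "A two group chi-square test with a 0.05 two-sided significance level will have 80% power" for the "difference between 30% vs. 5% proportion of O2sat dropping below 80" percent, "when the sample size in each group is 36".

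**The concern.** Randomising infants balances infants. It balances operators only if the operator is settled independently of the arm. Here the plan can be followed to the letter while the arm is known first and the resident is chosen second, and everyone in the room can see which device is in use.

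If residents were then matched to devices by seniority, the primary contrast would be device plus operator. Imbalance of this kind is systematic, so it does not average out as chance imbalance does. The training-level aims would suffer in the same way: if juniors did more of the video cases, a comparison of levels would be partly a comparison of devices. The unadjusted chi-square in section 7.0 would pass the first problem straight into the primary result.

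**Working it through.** **1. The plan's own figure.** Inputs from section 7.0: 30% and 5%, two-sided 0.05, 80% power, uncorrected chi-square. The mean rate is (0.30 + 0.05)/2 = 0.175.

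n = [1.960·√(2·0.175·0.825) + 0.842·√(0.30·0.70 + 0.05·0.95)]² / 0.25² = 35.1, rounded up to 36 per group.

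Power at 36 is 81.1% by the same approximation. The odds ratio is (0.05/0.95)/(0.30/0.70) = 0.123, matching the stated "odds ratio of 0.123". The sample size is not in question.

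**2. Method for the illustration.** Enumerate all pairs of binomial counts with 36 per arm, and sum the probability of those where the uncorrected Pearson chi-square reaches 3.841. For 30% vs 5% this exact power is 85.1%, which is the baseline used below.

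**3. Assumptions.** The documents give no risks by level, no mix of levels and no degree of steering. Assume half the cases are done by juniors overall, with direct-laryngoscopy risks of 45% (junior) and 15% (senior). These average to the plan's 30%.

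**4. No device effect, juniors steered to video.**

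| Junior share, video / direct | Direct risk | Video risk | Rejection |
|---|---|---|---|
| 50 / 50 | 30% | 30% | 5.2% |
| 60 / 40 | 0.4·45 + 0.6·15 = 27% | 0.6·45 + 0.4·15 = 33% | 8.9% |
| 70 / 30 | 0.3·45 + 0.7·15 = 24% | 0.7·45 + 0.3·15 = 36% | 20.4% |

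Direction matters. At 70/30, 20.3 points of the 20.4% falsely favour direct laryngoscopy and 0.1 point falsely favours C-MAC. If juniors were steered to direct laryngoscopy, the same totals would fall on the other side.

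**5. True six-fold effect (video risk = direct risk / 6), juniors steered to video.**

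| Junior share, video / direct | Direct risk | Video risk | Unadjusted power |
|---|---|---|---|
| 50 / 50 | 30% | 5% | 85.1% |
| 60 / 40 | 27% | 33/6 = 5.5% | 74.5% |
| 70 / 30 | 24% | 36/6 = 6% | 61.0% |

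**6. Stratifying by level.** A Mantel-Haenszel test stratified by level was simulated in the same model (200,000 runs). With no device effect, rejection is about 5% at both splits. With the six-fold effect, power is about 85% at 60/40 and 80% at 70/30.

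**7. Sensitivity of step 4 to the assumptions.**

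| Assumed junior / senior risk | 60/40 | 70/30 | 80/20 |
|---|---|---|---|
| 30% / 15% | 5.9% | 9.0% | 14.5% |
| 30% / 10% | 6.9% | 13.2% | – |
| 30% / 5% | 8.6% | 19.9% | 39.4% |

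**8. Training-level aim.** Assume no true effect of level, device rates of 30% and 5%, and 36 cases per level. If juniors do 60% of their cases by video and seniors 40%, juniors desaturate in 0.6·5 + 0.4·30 = 15% and seniors in 20%. That is a false difference of 5 points, rejected 8.6% of the time. At 70/30 the rates are 12.5% and 22.5%: a false difference of 10 points, rejected 19.9% of the time.

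**The case against.** **Steering is conjecture.** A reader might infer that staff do match residents to devices, or that the trial is biased. The documents support neither. Section 1.0 says that video helps staff to advise and step in; it does not say that juniors are given video cases. Section 4.0 reads as though a resident is already in the room. If a rota fixes that resident before randomisation, the mechanism largely disappears. The documents are silent either way, so the gap stands but the bias is only possible.

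**The direction may be misread.** A reader might take 20.4% as the chance of a spurious C-MAC success. Under the only motive the rationale suggests, juniors to video, nearly all of the excess runs against C-MAC. A false finding for the plan's hypothesis falls from 2.6% to 0.1% at 70/30. A spurious C-MAC success would need juniors steered to direct laryngoscopy, and nothing in the documents gives a reason for that.

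**Adjustment works for level.** A reader might also conclude that a level recorded after allocation is useless for adjustment. That is not so. Level is a fixed attribute of the resident and is already collected, and step 6 shows that stratification removes the bias due to level in this model. What remains is choice on skill within a level, which no analysis by level can remove. No stratified analysis is planned at present.

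**The size is assumed, and the training-level aims are observational anyway.** Both points are fair. Under a modest gradient and mild steering, the error moves only to 5.9%. Residents' levels are never randomised, so comparisons of levels stay observational after any fix. Device is recorded by design, however, and stratifying by it is simple.

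**Conclusion.** The concern holds as a gap in design and analysis. The plan sets no order between naming the resident and revealing an unmaskable device, it treats the operator as a possible driver of the outcome, and it plans only an unadjusted test. Operator selection after allocation is therefore allowed, and could distort the device comparison in either direction.

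The size depends wholly on assumptions. Across the risks and splits shown, type I error runs from about 6% (modest gradient, mild steering) to 39% (large gradient, strong steering). In the main illustration, unadjusted power falls by about 11 or 24 points (85.1 − 74.5; 85.1 − 61.0). Stratifying by level recovers all or most of that loss, but leaves any selection on skill within a level untouched. Preventing the selection is therefore better than relying on adjustment alone, and doing both costs little. The change should be made. The sample size of 36 per group is unaffected.

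**What to change.** **Section 5.0.** Add wording to this effect: *The intubating resident and his or her training level are entered in REDCap before the allocation is displayed. The named resident makes the first attempt. Any later change of first operator is recorded with the reason.* If a rota already fixes the resident before randomisation, say so as well. The freedom of staff to step in, as section 4.0 now has it, is unchanged.

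**Section 7.0.** Add a device comparison stratified by the pre-allocation training level (Mantel-Haenszel). Stratify the training-level comparisons by device. Report training level by arm.

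**Cost.** One REDCap field filled before allocation and a few protocol sentences; REDCap is already the trial database. The small downside is that the arm is known slightly later, so both devices must be at hand.

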#### **4.0 Study Procedures**

1. **Study design:** The study will be randomized, controlled, and prospective in design.
2. **Comparison groups** The two comparison groups will be:
  - a. **Conventional Laryngoscopy (DL), N = 35**  
Endotracheal intubation will be performed by conventional direct laryngoscopy.
  - b. **Video Laryngoscopy (CMAC), N = 37**  
Endotracheal intubation will be performed by video laryngoscopy with the C-MAC.
3. **Study and timeline of interventions**
  - a. **Preoperative:** All patients enrolled in this study will receive an intravenous catheter preoperatively.
  - b. **Intraoperative:** Subjects will all undergo induction of anesthesia by rapid sequence intubation. Upon arrival to the operating room, a new pulse oximeter probe will be placed on the patient's big toe. Orogastic suctioning with a 10 French Salem sump will be done with the patient supine, right and left lateral positions. Preoxygenation with 100% oxygen will be undertaken for approximately one minute. After pre-oxygenation, a rapid sequence induction will occur with Propofol 2.5mg/kg and Succinylcholine 2.5mg/kg IV. The resident will two-hand mask the patient and the staff anesthesiologist will manually ventilate the patient maintaining airway pressures less than 15mmHG. Approximately twenty seconds after administration of succinylcholine, direct laryngoscopy with a Miller 1 blade or a CMAC 0 blade will be undertaken. The patient will be intubated with a 3.0 cuffed endotracheal tube that has been loaded with a stylet. If the resident is having difficulty securing the airway, the staff may intervene at any point. The airway will be deemed secure when end tidal CO2 x 3 is seen, chest rise is adequate, and bilateral and equal breath sounds are heard. Anesthesia will be maintained with sevoflurane. The patient will be extubated at the conclusion of the case when he/she meets extubation criteria.
  - c. **Postoperative:** All patients will receive routine PACU care. Pain and anxiety scores will be recorded according to routine PACU practice. Medication for pain, nausea, and anxiety will be given according to the judgment of the anesthesiologist.
  - d. **Measured end-points:**
    - i. Level of resident training
    - ii. Desaturation below 80% during induction

- iii. Staff intervention needed for intubation
- iv. Number of intubation attempts

